## **Interventions Compared**

High-Touch. This approach leverages a personalized service design that includes payeremployed registered nurses and social workers to provide intensive, in-person/telephonic support and resources for eligible participants in their homes and/or communities for a minimum of four months following initial engagement. The health plan-based CT will focus on addressing the full range of health determinants that can impact an individual's health and health care and support information sharing with patients and providers through intervention that do not require access to mobile devices or the Internet.

*High-Tech.* By leveraging telehealth and remote monitoring technology to support selfdirected care management in real time, this approach uses less in-person resources. CT will focus on addressing the full range of health determinants that can impact an individual's health and health care through innovative approaches including virtual visits and access to mobile communications/applications for managing individual health and health care. 

**Optimal Discharge Planning (ODP).** Prior to the use of High-Touch and High-Tech interventions within our payer environment, all members with MCC who were hospitalized and at risk for rehospitalization were supported through the UPMC Health Plan's optimal discharge planning program, considered to be ODP for this study's purposes. After initial engagement via a phone call to the member, a Care Manager from the CT will have an in-home or telephonic visit with each individual to provide evidence-based support, including: detailed disease management and medication education; confirmation of and connection to family/caregiver support and resources; scheduling an ambulatory follow-up appointment; and a hand-off to a health plan-based telephonic care manager, as needed.

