## **Randomization Procedure**

The study will use web-based randomization to one of the three care strategies for those individuals who consent to participate in the study. The consent process may take place faceto-face with an eligible individual, or over the phone, providing that the individual consenting has received a paper or electronic copy of the consent form and enrollment materials to review. Once a member of the CT staff determines the individual's eligibility, they will enter in key identification information, independently or with support of the research team, and the system will then generate a Study ID (numeric identification number). A research team member will verify eligibility and the accuracy of the information entered with the CT staff and enrollee, and then the REDCap Cloud system will provide an assignment to an intervention arm. Randomization will be stratified by gender, type of insurance (Medicaid or Medicare-Medicaid), and technology/digital literacy, which will be assessed at time of enrollment and before randomization, to ensure that intervention arms are balanced with respect to these important variables. Within each stratum, random block sizes of 5 and 10 will be used to maximize balance between intervention groups while minimizing the ability to unmask investigators to the next treatment assignment, triggering an automated alert to CT staff regarding which intervention (care strategy) to implement for each participant and documented accordingly in HealthPlaNET, UPMC ISD's integrated health management software program. If a participant is unwilling to be randomized, they will be excluded from the study.

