## Covariates

Engagement in interventions will be assessed using the automatically generated usage statistics and administrative/ utilization data routinely collected for non-research purposes as part of insurance claims processing and existing payer-provider service delivery.

Patient characteristics will be obtained through self-report data and existing secondary administrative data on age, gender, race/ethnicity, and insurance type.

Technology/digital literacy will be measured using a series of questions from the Health Information National Trends Survey (HINTS) to assess comfort and experience with use of different. communication channels, including the Internet, to obtain vital health information for themselves and their loved ones.

Social support will be measured using the Interpersonal Support Evaluation List (ISEL), a 12-item measure designed to assess the perceived availability of three types of social support (appraisal, belonging, and tangible).

Health literacy will be measured using the first ten items of the All Aspects of Health Literacy Scale (AAHLS), a 13-item survey designed to assess functional, communicative, and critical health literacy. The final three items on the AAHLS are part of an 'empowerment scale' that is not related to the outcomes of this study.

Illness complexity will be measured using the age-adjusted Charlson Comorbidity Index (CCI) which was developed as a prognostic burden of comorbid disease and is currently used by the UPMC ISD. A score will be computed at baseline based on the previous 12 months of claims, adding assigned weights for specific diseases as classified by using International Classification of Diseases (ICD) diagnoses on claims records, and age adjusting by adding 1 point for every decade over 40 to the CCI score.

Socioeconomic status will be measured using the Area Deprivation Index (ADI), which uses 17 different socioeconomic indicators to determine a deprivation score for a given neighborhood. Scores are reported in the form of quintiles, with a higher quintile indicating a higher degree of deprivation.

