Our models will be based on an intent-to-treat principle as we do not expect large drop out or non-adherence. We will employ linear regression models for continuous outcomes, logistic regression for dichotomous outcomes, and Poisson regression or negative binomial models (in the case of over-inflated variance) for count outcomes. We will fit multivariate models with the key independent variable of interest being the main effect of treatment with main effects for additional covariates included to produce an adjusted estimate of the treatment effect. These covariates will be defined a priori and will be divided into two subgroups. The first set of clinically-important covariates will be included in all models including age, race, gender, insurance type, illness complexity, and socio-economic status. The second set of covariates will be defined as engagement in interventions, social support, health literacy, and technology literacy. To address Aim 2, separate models will be fit for each a priori defined heterogeneity of treatment group (HTE) subgroup of interest. As listed below, we will test the interaction of treatment with the covariate defining the HTE subgroup.

The objective of Aim 2 is to determine whether the intervention works better for some than for others. Our pre-specified analysis plan will examine differences in main outcomes for

several subgroups. These subgroups are determined by our stakeholders to be most relevant so that end results can meaningfully inform patients about what works best for whom, and in turn, better supports individuals with MCC as they navigate the health care system and make decisions about their care. Furthermore, in examining differential impact of the interventions based on these subgroups, providers, payers, and other decision makers can target resources in a manner that best meets the needs of those in services, reduces variations in practice, and improves health outcomes.

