We are only powering for the interactions with age, since we do not have any a-priori hypotheses about subgroup effects for the other variables. Those additional subgroups will clearly be labeled as exploratory and will only be examined further if the overall analysis is significant. We will conduct modeling as defined above to examine the HTE and will utilize contrasts from these regression models to make inferences about the heterogeneity. We will present both the treatment effect estimates, in terms of estimated odds or risk ratios for dichotomous or rate outcomes or the model coefficients for the continuous outcomes and measures of their variability in the form of confidence intervals. Two-sided tests of level 0.05 of the interactions between intervention and HTE subgroup will allow us to test the Aim 2 hypotheses.

For all the described models, we will focus on the 12-month outcome. Each of the above analyses will also be repeated using all follow-up outcomes collected as a secondary analysis using a mixed model with a random intercept to account for within-subject repeated measures and associated correlation. Significance tests from all regression models will all be assessed using likelihood ratio tests for logistic, Poisson, or, if applicable, negative binomial models or partial F-tests for linear regression.

Additionally, exploratory data analyses will include comparison of the following variables in the pre- versus post-COVID-19 time periods: a) demographics and primary outcomes at baseline, b) the primary outcomes over time, and c) patterns in missing data. If significant differences result, we will repeat the primary analysis by: a) adjusting for the demographic variables that can describe pre- and post-COVID-19 participants, b) include indicator variables for post-COVID-19 enrollment with and without interactions with time variables, and c) statistically account for missing patterns.

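### Engagement in the intervention, measured after randomization, is listed as an adjuster of the treatment effect and no models are named for it; technology literacy (a stratifier) and baseline scores are missing from the all-models covariates

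*Combined protocol and SAP*

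**What the plan says.** The Quantitative Analysis section opens its modelling text with "Our models will be based on an intent-to-treat principle". It then describes multivariable models with "main effects for additional covariates included to produce an adjusted estimate of the treatment effect", and divides those covariates into two sets fixed in advance.

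- First set: "included in all models including age, race, gender, insurance type, illness complexity, and socio-economic status".
- Second set: "The second set of covariates will be defined as engagement in interventions, social support, health literacy, and technology literacy". No model, and no primary, secondary or exploratory status, is attached to it.

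Under Covariates, engagement will be "assessed using the automatically generated usage statistics" together with administrative and utilization data. Interventions Compared describes three different services: at least four months of in-person and telephone support (High-Touch); "virtual visits and access to mobile communications/applications" (High-Tech); and, for Optimal Discharge Planning (ODP), a call, a visit and a hand-off if needed.

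For Aim 2 the plan says "We will conduct modeling as defined above to examine the HTE".

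The Randomization Procedure says "Randomization will be stratified by gender, type of insurance (Medicaid or Medicare-Medicaid), and technology/digital literacy", assessed before assignment. Study Design/Methodology has self-report data collected at baseline, and the planned COVID-19 comparison refers to primary outcomes at baseline. Neither covariate set contains a baseline outcome score.

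**The concern.** Use of an assigned program can begin only after assignment and may be part of how the program works. Conditioning on it does two things. It removes whatever part of the effect runs through engagement. It also makes the arms non-comparable on any unmeasured cause shared by engagement and outcome, such as motivation or frailty. The coefficient is then neither the intent-to-treat effect nor, without strong further assumptions, a direct effect.

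Readmission has an added timing problem. It is counted within 90 days of the last discharge before enrollment, while High-Touch support lasts at least four months and no window is set for engagement. Engagement could therefore accrue after the outcome or be altered by it.

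Because the role of the second set is open, an analyst could follow the plan and report either an intent-to-treat or an engagement-adjusted estimate as the treatment effect. The subgroup models are built the same way, so the gap carries into Aim 2.

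The lesser points concern efficiency. Leaving a stratification factor out of the model makes the test slightly conservative. Leaving out the baseline score gives up precision, mainly for PAM: the planned SF-36 comparison already has over 99% stated power, and readmission has no baseline score.

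**Working it through.** **Plan's own figure.** PAM, High-Touch vs High-Tech: difference 8 − 4 = 4, SD 20.9, 448 per arm, two-sided 0.05 (stated only for the interaction tests; assumed here). The noncentrality is 4 / (20.9 × √(2/448)) = 2.86, giving 81.6% power by noncentral t. The plan's 82% reproduces. It is an unadjusted calculation, so it does not settle the covariate question.

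**Engagement, true effect present.** All inputs beyond 4 and 20.9 are assumed. Let engagement be M = d·T + a·U + e (error SD 1), where T is arm and U an unmeasured shared cause. In SD units, let the outcome be Y = (1 − f)·τ·T + (f·τ/d)·M + 0.3·U + error, where τ is the total effect and f the share running through engagement. Since E[U | T, M] = a(M − dT)/(1 + a²), the coefficient of T given M is

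(1 − f)·τ − 0.3·a·d/(1 + a²).

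With τ = 4/20.9 = 0.191 and d = 0.5, the shared-cause term at a = ±0.3 is 0.3 × 0.3 × 0.5/1.09 = 0.0413 SD, or 0.86 points. The adjusted estimates of a true 4 points are:

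| f | a = +0.3 | a = 0 | a = −0.3 |
|---|---|---|---|
| 0.6 | 0.74 | 1.60 | 2.46 |
| 0.3 | 1.94 | 2.80 | 3.66 |

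A simulation of 2,000,000 subjects agrees within 0.06 points. In a separate simulation at trial size (2,000 runs, d = 0.5, no shared cause), power for the treatment coefficient with engagement in the model was about 79, 56, 28, 12 and 5% when 0, 25, 50, 75 and 100% of the effect ran through engagement. Without engagement it was about 82% throughout.

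**Engagement, no true effect.** Assume a shared cause correlated 0.5 with engagement and worth 5 PAM points per SD. The expected spurious coefficient is −5 × 0.5 × d, that is −0.75, −1.25 and −2.5 points for arm differences d of 0.3, 0.5 and 1.0 SD. Simulated type I error was about 9, 14 and 37%, against about 5% unadjusted.

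**Baseline PAM score.** The baseline to 12-month correlation r is assumed. If 20.9 is the SD of the 12-month score, the adjusted SD is 20.9·√(1 − r²). If it is the SD of change, the adjusted SD is 20.9·√((1 + r)/2), because the variance ratio is (1 − r²)/(2(1 − r)).

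| r | Power, 20.9 = SD of score | Power, 20.9 = SD of change |
|---|---|---|
| 0.3 | 85.1% | 94.4% |
| 0.5 | 91.1% | 91.1% |
| 0.7 | 98.0% | 87.4% |

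**Omitted stratifier.** Let ρ be its assumed correlation with PAM and k = √(1 − ρ²). By normal approximation, type I error when omitted is 2Φ(−1.96/k). Power is Φ((2.86 − 1.96)/k) omitted and Φ(2.86/k − 1.96) included.

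| ρ | Type I error, omitted | Power omitted | Power included |
|---|---|---|---|
| 0.1 | 4.89% | 81.8% | 82.1% |
| 0.2 | 4.55% | 82.2% | 83.2% |
| 0.3 | 3.99% | 82.8% | 85.1% |

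**The case against.** The strongest reply is that engagement adjustment is possible but not planned. The plan states intent-to-treat, sends only the first set to all models, and says elsewhere that modelling will explore moderators, which could be where the second set belongs. It stands that first-set models are unaffected and that the primary model is not shown to contain engagement. But the plan describes both sets as the covariates that produce the adjusted treatment effect, and no sentence confines the second set to exploratory work.

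The bias figures largely restate their inputs: with no shared cause, f = 0.6 must return 40% of the effect. The documents define no engagement scale common to the arms and do not say which arm would engage more; with less engagement in the better arm, the distortion could go the other way. No figure is given for readmission. All of this stands, so the figures illustrate the problem and do not predict its size.

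On the stratifier, what counts is the correlation left after the first-set covariates, which may be smaller than assumed. On the baseline score, the power section speaks of mean increases, so a change score, which already uses baseline, may be intended; the text names only the 12-month outcome. The power gains also start from the unadjusted 82%, so the gain over the covariate-adjusted model actually planned is probably smaller. These limits stand, and they are why both items are secondary.

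**Conclusion.** The point holds and should be fixed. A post-randomization variable is listed among the adjusters of the treatment effect, against the stated intent-to-treat principle, and the plan does not say where it will be used. This rests on the text alone.

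The size of the resulting bias is unknown. Under the assumptions above, a true 4-point PAM difference could be reported as anything from 0.7 to 3.7 points, and a null effect could be rejected 9 to 37% of the time.

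The two omissions affect precision, not bias. Under the assumed correlations, baseline adjustment raises PAM power from 82% to between 85% and 98%. Including the stratifier adds about 0.3 to 2.3 percentage points.

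**What to change.** 1. Remove engagement from every model that estimates a treatment effect, including the subgroup models and the repeated-measures versions. Report it by arm, and use it only in an analysis labelled exploratory.
2. Move technology/digital literacy into the first set, so that all three stratification factors are in all models.
3. Add the baseline value of the outcome to each linear model of a self-report score (SF-36, PAM, PROMIS, Q-LES-Q-18, PACIC). The treatment coefficient is then the same whether the outcome is the 12-month score or the change, so that ambiguity no longer affects the estimate.
4. State which models use social support and health literacy, and specify their baseline values.

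The cost is SAP wording and a few degrees of freedom. Technology literacy is assessed before randomization, and the primary self-report outcomes are available at baseline. The documents do not list the baseline instruments one by one or date the social support and health literacy measures, so confirm that these and the secondary scales were collected at baseline before finalizing items 3 and 4.

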## Study Design/Methodology

We have chosen an individual-level randomized design along with a pragmatic, mixed-methods approach to compare three integrated care approaches, High-Touch (in-person/telephonic supported), High-Tech (technology-supported) and ODP for Medicaid or dual-eligible adult members with MCC who reside in in Western, Central, or Eastern Pennsylvania (PA) and are at high risk for high utilization, including rehospitalization.

Quantitative data will be collected from several sources. Self-report data will be gathered at baseline and three additional timepoints (3-, 6-, 12-months) using REDCap Cloud, a secure data collection platform. Claims/administrative data will be collected from UPMC Insurance Services Division (UPMC ISD) to inform several outcomes and covariates. Claims data will be extracted at six months and 12 months to characterize participant service use through each participant's enrollment period, allowing for one full year of service-use observation.

Qualitative telephonic interviews will be conducted with a sample of participants and CT staff to examine perceived barriers and facilitators to efficient and effective implementation of the High-Touch and High-Tech approaches for delivering evidence-based integrated care at three timepoints (Participants: baseline, 3-, and 12-months; CT Staff: baseline, mid- and end-implementation period).

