#### **Primary Outcome Measures**

Patient activation will be assessed using the Patient Activation Measure (PAM), a 13-item scale that gauges individual knowledge, skills, and confidence essential to managing one's own health. In consideration of "straight-lined" answers in the PAM measure, (i.e., all 13 questions answered with "strongly disagree"), we plan to include all participant responses and conduct a sensitivity analysis. This is recommended by our study investigative team, including our Patient Partner Co-investigator.

Health status will be measured using the Health Survey (SF-36), a 36-item scale measuring functional health and well-being within eight domains, including physical functioning, physical ability to complete tasks, bodily pain, general health, vitality, social functioning, emotional ability to complete tasks, and mental health.

Subsequent 90-day rehospitalization will be measured using an all-cause readmission rate existing in UPMC ISD inpatient claims for physical and behavioral health service use within 90 days of the last hospital discharge prior to study enrollment. All-cause readmission does not include observation visits.

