# Inclusion/Exclusion Criteria

## **Inclusion Criteria**

Individuals who are (1) Medicaid or dual-eligible; (2) age 21 years and older; (3) insured through physical and/or behavioral health payers within the UPMC ISD; (4) identified as members high risk for high utilization including rehospitalization and have had an inpatient hospital stay within the last 30 days; (5) who have at least one physical health condition (e.g. cardiovascular disease, hypertension, COPD, diabetes) and at least one additional physical or behavioral health condition (e.g. depression, serious mental illness, substance abuse disorder); and (6) who reside in Pennsylvania.

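### The exploratory COVID-19 re-analysis codes period by enrolment date, so participants enrolled in the 12 months before the cut-off count as pre-COVID although their 12-month SF-36 and PAM fall after it

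*Combined protocol and SAP*

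**What the plan says.** All references are to the combined protocol and SAP.

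- **Screen.** Quantitative Analysis plans an exploratory "comparison of the following variables in the pre- versus post-COVID-19 time periods". It covers demographics and primary outcomes at baseline, primary outcomes over time, and missing-data patterns.
- **Re-analysis.** If differences are significant, the primary analysis is repeated in three ways: "adjusting for the demographic variables that can describe pre- and post-COVID-19 participants"; a step to "include indicator variables for post-COVID-19 enrollment with and without interactions with time variables"; and an account of missing-data patterns.
- **Main time point.** The same section states: "For all the described models, we will focus on the 12-month outcome". The mixed model using all follow-up visits is a secondary analysis.
- **Follow-up.** Study Design/Methodology sets self-report at baseline, 3, 6 and 12 months, and claims extraction "allowing for one full year of service-use observation".
- **Readmission.** Primary Outcome Measures counts readmissions "within 90 days of the last hospital discharge prior to study enrollment". Inclusion Criteria require that participants "have had an inpatient hospital stay within the last 30 days". Hypothesis 1a, however, refers to readmission at 12 months.

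No section gives a COVID-19 cut-off date, classifies an outcome by when it was measured, or says how to treat a participant whose follow-up spans the cut-off.

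**The concern.** The pandemic would act on an outcome at the calendar time when it is measured or accrues. The re-analysis dates exposure at month 0, while the outcome of main interest is at month 12. A participant enrolled 10 months before the cut-off has baseline, 3-month and 6-month data from before it and a 12-month score from after it, yet carries the pre-COVID code at every visit.

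What is at stake is how far the COVID-19 check can be trusted. With pandemic-era outcomes on the pre-COVID side of the contrast, the estimated pandemic effect shrinks towards zero and adjusting for the indicator removes only part of it. A small or null result from this check would then be weak reassurance.

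**Working it through.** The plan gives no figure for the COVID-19 analysis, so there is none to reproduce on this point. The evaluated sample does reproduce: 1,400 × (1 − 0.20) = 1,120.

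**Inputs from the documents**
- Start of implementation: 15 April 2018 (Study Timeline).
- End of accrual: not dated. Data Safety Monitoring says the board closes in spring 2022 once enrolment goals are met.
- 1,400 enrolled and 1,120 evaluated at 12 months (Synopsis; Sample Size and Power Calculations).

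**Assumptions**
- Even accrual over about 48 months.
- A cut-off about 23 months into accrual.
- Attrition spread evenly over calendar time.

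**Step 1: who straddles the cut-off at 12 months**
- Share of all participants: 12/48 = 25%. This does not depend on the cut-off, provided that the preceding 12 months lie within accrual.
- Number evaluated: 0.25 × 1,120 = 280.
- Share of those coded pre-COVID: f = 12/23 = 52%.

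**Step 2: SF-36 and PAM at 12 months.** Let a pandemic shift D apply to every score measured after the cut-off, and let μ be the mean without it.
- Mean of those coded post: μ + D.
- Mean of those coded pre: μ + fD.
- Contrast: (1 − f)D = (1 − 12/23)D = 0.48D.

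**Step 3: the interactions with time.** The single-time-point 12-month model has no follow-up time term. In the mixed model, an enrolment-by-visit term still pools, at each visit, people coded pre who were measured on either side of the cut-off:
- 3 months: 1 − 3/23 = 0.87.
- 6 months: 1 − 6/23 = 0.74.
- 12 months: 1 − 12/23 = 0.48.

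A constant shift D would therefore look as if it faded over follow-up.

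**Step 4: claims outcomes accumulated over 12 months.** Under even accrual, straddling participants have on average half of their year after the cut-off. With a constant shift in rate:
- Contamination of the pre group: 0.52 × 0.5 = 0.26.
- Contrast retained: 1 − 0.26 = 74%.

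This is approximate for a yes/no readmission outcome.

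**Step 5: the 90-day readmission measure.** The window starts at a discharge up to about 30 days before enrolment, so it ends about 60 to 90 days after enrolment.
- Share of all participants: 2/48 = 4% to 3/48 = 6%.
- Share of the pre group: 2/23 = 9% to 3/23 = 13%.

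**Step 6: sensitivity, counted in days.** Accrual from 15 April 2018; cut-off varied from 1 March to 1 April 2020 (assumed).

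| Accrual end (assumed) | Accrual days | Straddling at 12 months | Of 1,120 |
|---|---|---|---|
| 31 Dec 2021 | 1,356 | 365/1,356 = 27% | 301 |
| 31 Mar 2022 | 1,446 | 365/1,446 = 25% | 283 |
| 31 Dec 2022 | 1,721 | 365/1,721 = 21% | 238 |

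The share of the pre group runs from 365/717 = 51% to 365/686 = 53%. If accrual was uneven and that share lay between 30% and 70%, the SF-36 or PAM contrast would show 0.7D to 0.3D.

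**The case against.** **The screen may be sound.** A reader might infer that the miscoding decides whether the re-analysis runs at all. The text does not support that. The screen is worded by time periods, which can be read as calendar time; enrolment is named only in the re-analysis step. The comparison of outcomes over time is also only one of three triggers, and for the baseline trigger enrolment date is the right classifier. This objection stands.

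**The wording is loose.** The indicators and time variables are plural and undefined. Several enrolment indicators could encode a straddling group, and a calendar-time variable is not excluded. This stands only in part: the text names one basis for classification, enrolment after COVID-19, and nothing in it points to a straddling group or to calendar time.

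**The dilution is not uniform.** A reader might take the halving, or the idea that everyone enrolled in the preceding year is miscoded, as applying to every outcome. It fits survey scores taken at one time. It does not fit 12-month claims totals or the 90-day measure. Nor should the 25% be applied to all 1,400 enrolled when the plan expects 1,120 to be evaluated at 12 months.

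**The trial's conclusion is little affected.** The work is exploratory and conditional. Arms are randomised concurrently in blocks of 5 and 10, so calendar period should be balanced across arms. Enrolment period is also a legitimate baseline covariate for changes in case mix. All of this stands.

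**Actual survey date is post-randomisation** and may depend on arm through late response. This stands, and it favours scheduled dates in any recoding.

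**Conclusion.** The point holds for the re-analysis step. Coding period by enrolment puts a substantial block of 12-month outcomes measured after the cut-off on the pre-COVID side, and the planned time interactions do not separate them. The sizes in steps 1 to 5 depend on the assumed accrual pattern and cut-off, which the documents do not give; step 6 shows the range. The effect is large for SF-36 and PAM at 12 months, moderate for 12-month claims outcomes and small for 90-day readmission.

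The consequence is limited to a diluted COVID-19 estimate and an incomplete adjustment in an exploratory check. A reader might go on to infer that the comparison of High-Touch, High-Tech and ODP is biased. The documents do not support that, because randomisation ran concurrently in all arms. Whether the screen shares the problem cannot be settled from its wording. This is an inexpensive improvement, not a threat to the main result.

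**What to change.** - State the COVID-19 cut-off date.
- For 12-month survey models, use three groups defined by enrolment date and scheduled 12-month visit: outcome before the cut-off; enrolled before with outcome after; enrolled after.
- In the mixed model, use a time-varying period indicator based on scheduled visit date, so that it does not depend on when participants respond after randomisation.
- For claims outcomes, use the share of the observation window that falls after the cut-off.
- Use the same definition in the screen for outcomes over time, and keep the enrolment indicator for baseline comparisons.

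The cost is a change of SAP wording and period variables derived from dates already held. There are two small downsides: one more category in an exploratory model, and slight residual misclassification when a survey is completed well after its scheduled date.
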